8.1.2 Route and method of administration

Patients will receive IV olipudase alfa over the same time period as in their original study. The length of the infusion time may be adjusted based on the patient's tolerance of the infusion.

During the study, pediatric patients who reach adult age (18 years old) will receive the adult infusion volume.

See [Section 8.1.5](#) for information on dose adjustments following dosing delays or missed doses.

8.1.3 Dosing considerations

Patients will receive the same olipudase alfa dose every 2 weeks, provided they have not missed more than 1 biweekly dose between studies.

Dosing will be based on an individual patient's mass (ie, weight) as outlined in [Section 8.1.1](#). For patients who participated in the DFI13412 study and who had a body mass index (BMI) >30 , the dose will be based on the mass (in kilograms) corresponding to a BMI of 30 given the specific patient's height.

8.1.4 Dose adjustments

Dose adjustments may also be considered at any time in consultation with the sponsor but may be recommended based on current safety or efficacy analysis results obtained from completed or ongoing studies of olipudase alfa.

8.1.5 Dosing delays or missed doses

Dose reintroduction regimens may be required for patients who have missed more than 1 dose between studies or during this study (LTS13632), depending on their usual dose. For patients receiving home infusions who have missed 2 or fewer doses, the investigator can decide whether reintroduction should occur at the hospital/study site via home infusion. For patients who have missed 3 or more doses ≥ 0.6 mg/kg, reintroduction of olipudase alfa should occur at the hospital/study site. If the site visit is not possible due to site closure or extenuating circumstances that prevent an in-person site visit (eg, during COVID-19 pandemic), reintroduction may be done via home infusion, if the patient has previously been approved for home infusion.

Patients who require dose reintroduction will have these assessments at each infusion until reaching their usual dose of olipudase alfa:

- Before infusion: vital sign measurements, liver function tests (LFTs), hematology tests and safety biomarkers.
- Immediately after infusion: vital sign measurements.
- 24 hours after infusion: vital sign measurements, LFTs, hematology and safety biomarkers
- 48 hours after infusion: vital sign measurements, LFTs and safety biomarkers.

The 48 hours post-infusion assessments will no longer be assessed after the cutoff date for a planned second database lock of the study for purpose of regulatory submissions in 2021.

During the dose escalation period, for transaminases assessed after infusion, if any AST or ALT value is $>2x$ baseline and $>ULN$, the test should be repeated prior to the next scheduled infusion. Depending on the test results, the dose can be adjusted (repeated or reduced) or treatment can be withheld to allow additional transaminase monitoring, based on the physician's clinical judgment.

Baseline is defined as the following:

- For initial dose escalation: last values prior to first dose of olipudase alfa
- For dose re-escalation: last values prior to the first re-escalation dose

8.1.6 Dose stopping criteria

If any of the following AEs occur, dosing will be temporarily stopped for the specific patient who experienced the AE:

- Any SAE, not related to the patient's underlying condition and considered related to the study treatment.
- Any increase in AST, ALT, total bilirubin, or alkaline phosphatase (AP) >3 x baseline (prior to olipudase alfa therapy, ie, baseline value from the primary study) and $>$ the upper limit of normal (ULN).
- Any increase in total bilirubin or AP >1.5 x baseline, in the presence of AST or ALT >2 x ULN.
- Any increase in ALT or AST >3 x ULN combined with an increase in ALT or AST >2 x baseline (prior to olipudase alfa therapy), with symptoms of fatigue, nausea, vomiting, right upper quadrant pain or tenderness, fever, rash, or eosinophilia ($>$ ULN).
- Any AE that, in the opinion of the investigator or sponsor, raises significant concern regarding the safety of olipudase alfa at the administered dose.

8.1.7 Study interruption criteria

If either of these criteria are met,

- 2 patients develop the same severe AE that is not related to their underlying condition, or
- A death occurs that is assessed as related or possibly related to olipudase alfa, an ad hoc DMC meeting will be held to review the safety data and provide its recommendations to the sponsor regarding further patient treatment.

After consideration of DMC recommendations, final decisions regarding discontinuation of study drug for all or selected clinical trial patients will be made by the Sponsor.

In the event a significant safety concern arises, the Sponsor may immediately decide to discontinue study drug dosing in all clinical trial patients prior to receipt of DMC recommendation.

If the study is temporarily or permanently halted, the Sponsor will notify the health authorities of the halt by a substantial amendment in regions where this applies.

8.1.8 Treatment discontinuation

A patient's study treatment may be discontinued at any time at the patient's request or at the discretion of the investigator or sponsor. The following may be justifiable reasons for the investigator or sponsor to discontinue a patient from treatment:

- The patient was erroneously included in the study (ie, was found to not have met the inclusion/exclusion criterion).

- The patient is unable to comply with the requirements of the protocol.
- The patient participates in another interventional investigational study
- In the opinion of the investigator, the patient is no longer deriving clinical benefit.
- Pregnancy

Patients who received at least 1 dose of investigational product and who are withdrawn from the study will be asked to complete all discontinuation assessments prior to withdrawal (as detailed in [Section 1.1](#) and [Section 1.2](#) [adults] and [Section 1.4](#) and [Section 1.5](#) [pediatric patients]) and will receive a safety follow up telephone call from the study site 30 to 37 days after the final administration of olipudase alfa.

The investigator will document the reason(s) for treatment discontinuation/study withdrawal on the case report form (CRF).

8.2 BLINDING PROCEDURES

Not applicable. This is a single-arm, open-label study design.

8.3 PACKAGING AND LABELING

Olipudase alfa is packaged and labeled according to Good Manufacturing Practices and local regulatory specifications and requirements. Refer to the corresponding manual for additional details.

8.4 STORAGE CONDITIONS AND SHELF LIFE

All clinical trial material must be kept in a secure area with restricted access and be stored under adequate refrigerated temperature conditions (2°C to 8°C [36°F to 46°F]). Temperature excursions will be handled as described in the corresponding manual.

It is recommended that the reconstituted product be used immediately after reconstitution. Additional stability data are provided in the corresponding manual.

8.5 RESPONSIBILITIES

The investigator, the hospital pharmacist, or other personnel allowed to store and dispense the investigational medicinal product (IMP) will be responsible for ensuring that the study drug used in the clinical trial is securely maintained as specified by the sponsor and in accordance with applicable regulatory requirements.

All IMP will be dispensed in accordance with the investigator's prescription and it is the investigator's responsibility to ensure that an accurate record of IMP issued and returned is maintained.

Any quality issue noticed with the receipt or use of an IMP (deficiency in condition, appearance, pertaining documentation, labeling, expiration date, etc) should be promptly notified to the sponsor. Some deficiencies may be recorded through a complaint procedure.

A potential defect in the quality of IMP may be subject to initiation of a recall procedure by the sponsor. In this case, the investigator will be responsible for promptly addressing any request made by the sponsor in order to recall IMP and eliminate potential hazards.

Under no circumstances will the investigator supply IMP to a third party, allow the IMP to be used other than as directed by this clinical trial protocol, or dispose of IMP in any other manner.

8.5.1 Treatment accountability and compliance

Compliance to the treatment regimen will be monitored in terms of the percentage of scheduled infusions the patient receives through the treatment period. No infusions should be missed. Noncompliance is defined as missing 2 consecutive infusions or 4 total infusions per each 12-month period throughout the treatment period. As they are identified, the investigator should discuss noncompliant patients on a case by case basis with the sponsor's medical monitor (or designee).

8.5.2 Return and/or destruction of treatments

Reconciliation of study drug must be performed at the site by the investigator and the monitoring team using treatment log forms and documented on center study drug inventory countersigned by the investigator and the monitoring team.

If appropriate, a written authorization for destruction will be provided by the sponsor clinical trial team once the reconciliation is achieved. Investigational medicinal product destruction may be performed at the site depending on study drug specificities and local requirements; alternatively, study drug may be returned to the sponsor for destruction.

8.6 CONCOMITANT MEDICATION

Medications and therapeutic procedures received by the patient in the 30 days prior to their providing written and signed informed consent or assent until the final visit for this study will be recorded on the concomitant medication CRF, as appropriate.

Prior and concomitant medications will be coded according to the World Health Organization Drug Dictionary.

- Prior medications will be defined as medications that were taken prior to the first infusion of olipudase alfa.
- Concomitant medications will be defined as medications that are taken after providing informed consent in this study.

During the study, prohibited medications include those that may decrease olipudase alfa activity (eg, chlorpromazine, tricyclic anti-depressants [eg, imipramine or desipramine]). See the most recent version of the study manual for a list of concomitant medications that may decrease olipudase alfa activity.

Cationic amphiphilic antihistamines, such as loratadine, desloratadine, astemizole, ebastine, terfenadine, and clemastine, may decrease olipudase alfa activity. Therefore, the need for their use in oral or IV administration should be carefully considered. There is no restriction on topical antihistamines.

Certain medications and herbal supplements can be hepatotoxic or can cause or prolong bleeding, and should not be taken within 10 days before and 3 days after the biopsy procedure (only patients who previously participated in the DFI13412 study). Potentially hepatotoxic medications or herbal supplements include, but are not limited to, 3-hydroxy-3-methylglutaryl-coenzyme A reductase inhibitors, erythromycin, valproic acid, antidepressants, kava, and echinacea. Medications that may cause or prolong bleeding include, but are not limited to, anticoagulants, ibuprofen, aspirin, garlic supplements, ginkgo, and ginseng.

These lists of prohibited medications and herbal supplements may be incomplete. The investigator may also prohibit medications and products not listed here. Therefore, the investigator must review all medications and products for every patient. For more information on medications and herbal supplements that may decrease olipudase alfa activity or may be hepatotoxic, refer to the most recent version of the study manual.

Pretreatment in general is not recommended for prophylactic management of IARs. For patients who experience moderate to severe or recurrent IARs (as defined in [Section 10.5.1.3.2](#)) suggestive of hypersensitivity, pretreatment regimens (eg, antihistamines, antipyretics, glucocorticoids) may be prescribed by the investigator as per clinical judgment. In particular, the need for cationic amphiphilic antihistamines administered orally or IV should be carefully considered given the potential risk for functional inhibition of olipudase alfa activity by such drugs.

8.6.1 Treatment of infusion-associated reactions

For management of mild IARs, infusion rate reductions (eg, reduced to half the rate) or temporary interruptions may mitigate the reaction. For moderate to severe or recurrent IARs, the investigator may consider the use of pretreatment medications (eg, antihistamines, antipyretics, and/or glucocorticoids), if the symptoms are suggestive of hypersensitivity reaction, in addition to infusion rate reductions, interruptions, or discontinuation. In particular, the need for cationic amphiphilic antihistamines administered orally or IV should be carefully considered given the potential risk for functional inhibition of olipudase alfa activity by such drugs.

Patients experiencing symptoms suggestive of hypersensitivity reactions, including anaphylactic or anaphylactoid reactions, during olipudase alfa infusion should be managed according to the general standards of care consistent with the treatment of such reactions. If anaphylaxis or other severe allergic reactions occur, immediate discontinuation of the infusion should be considered, and appropriate medical treatment should be initiated. Because of the potential for severe IARs, appropriate medical personnel and equipment to perform resuscitation must be readily available in the event of a hypersensitivity reaction.

9 ASSESSMENT OF INVESTIGATIONAL MEDICINAL PRODUCT

The term “pediatric patients only” means patients coming from the original pediatric trial, DFI13803. Some of these patients will reach adult age (18 years old) while in this study. These patients will be adults by age, but they will remain part of the “pediatric patient” cohort.

9.1 ENDPOINTS

9.1.1 Primary endpoint

Primary safety endpoints pertaining to the safety and tolerability of olipudase alfa, as described in [Section 9.1.4](#) through [Section 9.1.15](#), include:

- Assessment of AEs/treatment-emergent AEs (TEAEs), including IARs (eg, cytokine release syndrome [CRS], APRs), and adverse events of special interest [AESIs]).
- Complete physical examinations.
- Extended neurological examinations.
- Abbreviated physical examinations.
- Weight.
- Height (pediatric patients only).
- Vital sign measurements.
- Clinical laboratory tests:
 - Clinical chemistry,
 - LFTs,
 - Hematology,
 - Coagulation studies,
 - Urinalysis,
 - Urine pregnancy test (women of childbearing potential only).
- ECGs.
- Echocardiogram with Doppler.
- Liver biopsy (only patients who previously participated in the DFI13412 study).
- Liver ultrasound with Doppler (only patients who previously participated in DFI13803).

- Safety biomarkers:
 - High-sensitivity C-reactive protein (hsCRP),
 - Iron,
 - Ferritin,
 - Cardiac troponin I,
 - Interleukin (IL) 6,
 - IL 8,
 - Calcitonin,
 - Plasma ceramide.
- Immune response assessments.

A site physician will assess safety findings as normal, abnormal but not clinically significant (NCS), or abnormal and clinically significant (CS). Any abnormal findings that meet the definition of an AE per [Section 10.5.1](#) will be recorded on the AE CRF.

The analysis of safety is described in [Section 11.6.3](#).

9.1.2 Secondary endpoints (efficacy)

Secondary endpoints (efficacy), as described in [Section 9.2.1](#) through [Section 9.2.9](#) include:

- Abdominal magnetic resonance imaging (MRI) to evaluate improvements in spleen and liver volume.
- Pulmonary imaging:
 - High resolution computed tomography (HRCT),
 - Chest X-rays (at selected sites).
- Pulmonary function tests (PFTs).
- Hematology:
 - Hemoglobin,
 - Platelet count.
- Lipid profile:
 - Total cholesterol,
 - High-density lipoprotein (HDL),
 - Low-density lipoprotein (LDL),
 - Very low-density lipoprotein (VLDL),
 - Triglycerides,
 - Apolipoprotein B (ApoB),
 - Apo A,
 - Lipoprotein(a).
- Hand X-ray (pediatric patients only).

- Linear patient growth by height Z-score (pediatric patients only).
- Adult health outcome questionnaires:
 - Brief Fatigue Inventory (BFI),
 - Brief Pain Inventory Short Form (BPI-SF),
 - Chronic Respiratory Disease Questionnaire Self-administered Standardized (SFCRQ SAS),
 - Short Form 36 (SF-36),
 - Niemann-Pick B Health Assessment Questionnaire (NPB-HAQv2), version 2.
- Pediatric health outcome questionnaires:
 - Pediatric Quality of Life (PedsQL),
 - PedsQL Multidimensional fatigue scale,
 - PedsQL Pediatric Pain Questionnaire.
- An additional questionnaire about home infusion experience may be added for patients who received home infusion treatment for at least one year.

Efficacy analyses are described in [Section 11.6.2](#).

9.1.3 Other endpoints

Other endpoints, as described in [Section 9.3.1](#) through [Section 9.3.9](#), include:

- Physician global assessment of change.
- Cognitive and adaptive function (for pediatric patients who performed the assessments in DFI13803):
 - Development Profile-Third Edition (DP-3),
 - Adaptive Behavior Assessment System (ABAS).
- Cycle ergometry to evaluate exercise capacity.
- Efficacy biomarkers, including, but not limited to:
 - Serum chitotriosidase,
 - CCL18
- Bone disease assessments (only patients who previously participated in the DFI13412 study):
 - Lumbar spine MRI for bone marrow burden score,
 - Bilateral femur MRI for bone marrow burden score,
 - Lumbar spine by dual-energy X-ray absorptiometry (DXA) for bone mineral density (BMD) T-score and Z-score,
 - Bilateral femurs by DXA for BMD T-score and Z-score.

- Bone biomarkers:
 - AP,
 - C-telopeptide levels.
- Tanner staging (pediatric study DFI13803 patients only).
- Photographs (optional).
- Pharmacokinetics.
- Pharmacodynamics (metabolite levels in plasma and/or dried blood spot (DBS) [eg, sphingomyelin, lysosphingomyelin]).
- Plasma ceramide.
- Sphingomyelin levels in liver tissue obtained by liver biopsy (only patients who previously participated in the DFI13412 study).

Efficacy analyses are described in [Section 11.6.2](#).

Pharmacokinetic parameters and pharmacodynamics (PD) will be assessed as described in [Section 9.3.8](#) and [Section 9.3.9](#), respectively. Pharmacokinetic and PD analyses are described in [Section 11.6.4](#).

9.1.4 Safety assessments

See [Section 10.5.1](#) for more details about AEs.

9.1.5 Complete physical examination

A complete physical examination will be performed prior to infusion at the time points specified in [Section 1.1](#) through [Section 1.5](#). A complete physical examination will include assessment of the patient's general appearance, general neurological status, skin, head, eyes, ears, nose, throat, lymph nodes, heart, lungs, abdomen, and extremities/joints.

9.1.6 Extended neurological examination

9.1.6.1 Extended neurological examination in adults

The neurological examination in adults will include, but is not limited to, mental status, cranial nerves, muscle strength, sensation, deep-tendon reflexes, coordination, and gait.

9.1.6.2 Extended neurological examination in pediatric patients

The neurological examination in pediatric patients will include, but is not limited to, mental status, posture, cranial nerves, motor system including muscle atrophy, tone and power, reflexes, sensory system, coordination, gait, and age-appropriate responses. If possible, the neurological examination should be performed by the same neurologist who performed it in the DFI13803

study. Also, if possible, the neurological examination should be performed by the same neurologist throughout the study.

9.1.7 Abbreviated physical examination

An abbreviated physical examination of the patient's general appearance only will be performed before and after infusion at the time points specified in [Section 1.1](#) through [Section 1.5](#). Patients will be assessed for body weight, height, and calculated BMI at the time points specified in [Section 1.1](#) through [Section 1.5](#).

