11.6.3.2 Laboratory data and vital sign measurements

11.6.3.2.1 Physical examinations, vital sign measurements, electrocardiograms, and echocardiograms

Observed values and changes from baseline (as applicable) will be summarized descriptively overall and by highest tolerated dose and/or by dose received prior to evaluation. Outlier summaries for the ECG parameters (eg, QTc) will be created for the safety set.

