#### **2.1.4.14 Height Z-score (Patients from pediatric study DFI13803)**

This endpoint, reflecting failure to thrive, is specific to patients transitioning from pediatric study DFI13803. Patient height is collected at screening and within 24 hours prior to every infusion visit in the original study, then every 6 months in the extension study. Z-score is the normalized value when compared to mean and standard deviation of height of children considered to have normal growth, based on gender and age: [height – normal mean(height)]/normal SD (height). The normal levels are provided by World Health Organization list from 2007. Height z-score will be calculated and categorized using the number and percentage of patients in <= -4, > -4 to <= -3.5, > -3.5 to <= -3, > -3 to <= -2.5, > -2.5 to <= -2, > -2 to <= -1.5, > -1.5 to <= -1 and > -1.

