#### **2.4.2 Baseline safety parameters**

Baseline for safety parameters (weight, height, body mass index (BMI), physical exam, vital signs, echocardiograms, immune response assessments, and safety biomarkers) in general is defined as the last available non-missing value for the parameter before the first infusion in the original study. Most of the baseline values will thus be from the Day 1/Week 0 pre-infusion assessments in the original study, with the exception of hematology parameters and possibly electrocardiogram (ECG). Hematology samples are collected for pediatric patients twice at screening and twice on first infusion visit, once before and once after the first infusion; for adult patients, they are collected once at screening, twice before infusion on first infusion visit and one after the first infusion. The average of all measurements taken before the first infusion will serve as the baseline. Another exception may be the ECG parameters – Day 1/Week 0 (the first infusion visit in the original study) is to collect ECG in triplicate before the infusion; if 2 or more than 2 of these triplicate collections of ECG are before the first infusion, the average of these ECG parameter results will be considered as the baseline value; otherwise, the baseline value of ECG parameters will be taken from the latest observation before the first infusion.

Baseline safety data will be presented along with subsequent values assessed during or after olipudase alfa dosing using safety population.

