#### **2.4.7.6 *Physical examinations***

Complete physical examination (except overall neurological exam - please see [Section 2.4.7.7](#)) will be classified as normal or abnormal. Shift tables will be provided. A listing of the abbreviated physical examination data will be provided.

Observed values and change from baseline for weight, height and BMI will be summarized for all scheduled time points.

For patients from the pediatric study DFI1303, the age-appropriate growth in height is a matter of efficacy; please see [Section 2.4.8.14](#) for analysis of height z-scores.

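### Children's weight and BMI are summarised only as raw values and change from a pre-treatment baseline, so poor weight gain short of net loss is unlikely to show

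*Protocol*

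**What the plan says.** **Collection.** Protocol 9.1.7 states: "Patients will be assessed for body weight, height, and calculated BMI at the time points specified in" the flow charts. It sets no analysis.

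**Status of the measures.** Protocol 9.1.1 opens its list with "Primary safety endpoints pertaining to the safety and tolerability of olipudase alfa, as described in" the sections that follow, and weight is on that list. BMI is not. SAP 2.4.2 does treat BMI as a safety measure, since its definition begins "Baseline for safety parameters (weight, height, body mass index (BMI), physical exam, vital signs".

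**Baseline.** SAP 2.4.2 sets it as the "last available non-missing value for the parameter before the first infusion in the original study", with exceptions for hematology and possibly ECG only.

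**Analysis.** SAP 2.4.7.6 states: "Observed values and change from baseline for weight, height and BMI will be summarized for all scheduled time points". Protocol 11.6.3.2.1 is no more specific: "Observed values and changes from baseline (as applicable) will be summarized descriptively overall" and by dose. Neither document gives a weight-for-age or BMI-for-age score, percentile or reference. SAP Appendix A sets abnormality limits for laboratory tests, vital signs and ECG, but none for weight or BMI.

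**Height is handled differently.** Under SAP 2.1.4.14, "Z-score is the normalized value when compared to mean and standard deviation of height of children considered to have normal growth", by gender and age, using a World Health Organization list from 2007. SAP 2.4.8.14 then analyses the change by ANCOVA. The SAP describes this endpoint as reflecting failure to thrive.

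**The concern.** About 20 of the expected 25 patients are children, followed for years. A raw weight change in a growing child is mostly growth, so its sign and size say little about whether the child gained as expected. A table of mean changes by visit would look favourable even if several children were dropping away from their expected weight, because the expected weight is never displayed.

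The SAP recognises this problem elsewhere. It standardises height by age and sex, expresses lung function as percent predicted (2.1.4.2), compares bone age with actual age (2.4.8.12), and sets many pediatric limits in Appendix A by age band. Weight is the primary safety endpoint left without any such adjustment, in a disease whose features include growth retardation (Protocol 4.1).

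**Working it through.** The plan states no figure to reproduce: sample size is the number of rollover patients, and Protocol 11.6.3 excludes formal testing of safety data. The check is an illustration of what the planned summary would display.

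**Inputs from the documents**
- Length of the original pediatric study: 64 weeks (SAP 2.4).
- Minimum pediatric treatment in this study: 3 years (Protocol 6.3).
- Minimum planned time from baseline: 64/52 + 3 = 4.23 years.

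**Inputs that are assumptions**
- Normal weight gain g: 2 to 3 kg per year.
- One SD of weight for age at the later visit: 3 to 5 kg.
- The child is at the median at baseline and falls k SD by time T.

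These ranges are generic. They are not specific to infants, children or adolescents.

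**Formula:** raw change = g × T − k × SD. The lowest value uses g = 2 and SD = 5; the highest uses g = 3 and SD = 3.

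| Fall | Years from baseline | Lowest raw change | Highest raw change |
|---|---|---|---|
| 1 SD | 3 | 2×3 − 5 = +1 kg | 3×3 − 3 = +6 kg |
| 1 SD | 5 | 2×5 − 5 = +5 kg | 3×5 − 3 = +12 kg |
| 2 SD | 3 | 2×3 − 10 = −4 kg | 3×3 − 6 = +3 kg |
| 2 SD | 5 | 2×5 − 10 = 0 kg | 3×5 − 6 = +9 kg |

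A 1 SD fall is never negative. A 2 SD fall can be negative at 3 years but not at 5.

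**Second model, with a proportional shortfall s:** raw change = g × (1 − s) × T, with g widened to 2-5 kg per year and T = 4.23.
- s = 50%: 2 × 0.5 × 4.23 = +4.2 kg to 5 × 0.5 × 4.23 = +10.6 kg. The child is the same amount below expected weight.
- s = 75%: 2 × 0.25 × 4.23 = +2.1 kg to 5 × 0.25 × 4.23 = +5.3 kg. The child is 6.3 to 15.9 kg below expected.

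In this model only net loss below the pre-treatment weight gives a negative change.

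**BMI.** The argument is not the same. BMI divides by height squared, so poor weight gain with normal height lowers it. The difficulty is that expected BMI varies with age, so a raw change has no fixed value that means normal.

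**What a Z-score summary would offer.** Under normal growth the expected change is 0. With an assumed SD of change of 0.5 to 1.0, the 95% half-width of the mean change is 1.96 × SD/√n. That is 0.22 to 0.44 for n = 20 (protocol) and 0.28 to 0.57 for n = 12 (SAP).

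**The case against.** A reader might infer that the plan cannot show harm, or that the weight table will look reassuring whatever the drug does. The documents do not support that:
- The illustration itself gives −4 kg at the low end for a 2 SD fall at 3 years, so a severe fall can appear as net loss.
- Under Protocol 9.1.1 a site physician rates safety findings, and abnormal ones meeting the adverse event definition are recorded as such. They would then reach the tables in SAP 2.4.7.1.2.
- SAP 2.4 provides summaries by original study and pediatric age cohort, and listings behind every table, so individual courses can be traced.
- Height Z-score covers stunting, SAP 2.4.7.6 adds normal/abnormal shift tables for the complete physical examination, and an independent committee reviews safety data (Protocol 6.4).

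These points defeat the absolute reading, but they do not replace the missing summary. Age cohorts are wide and carry no expected value, height does not measure weight, and no weight-for-age criterion prompts a site to report.

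A reader might also infer that growth hides poor weight gain within BMI, or that BMI is a primary endpoint. Neither is right, for the reasons given above. Nor is Protocol 9.1.7 at fault, since it concerns collection only.

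Two further objections stand. The study is single-arm and growth retardation belongs to the disease, so a falling Z-score could not by itself be attributed to the drug. The documents name a growth reference for height only, so whether that source covers weight and BMI at these patients' ages cannot be confirmed from them.

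**Conclusion.** The point holds as a weakness in how a primary safety endpoint is displayed. For former DFI13803 patients, raw weight change from a baseline at least about 4.2 years old (at the minimum planned follow-up) is dominated by growth and never shows the gap to expected weight. Poor gain short of net loss is unlikely to be visible in the summary. For BMI the narrower conclusion applies: raw change lacks a fixed reference.

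The size rests on the assumed gain and SD. Across those ranges masking is substantial but incomplete, and adverse event reporting, listings and height Z-score give partial cover. No error rate or hypothesis test is affected, because safety analysis is descriptive. The change is worth making because it is cheap and consistent with the SAP's own treatment of height.

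**What to change.** In SAP 2.4.7.6, for former DFI13803 patients:
- Add age- and sex-standardised weight and BMI Z-scores, giving observed value and change from baseline by scheduled visit and age cohort.
- Add the number of patients whose Z-score has fallen by 1 SD or more from baseline.
- Name the reference used for each measure and its age limits, and report how many patients fall outside them at each visit.
- Keep kg and kg/m² as supportive summaries for these patients, and unchanged for the adult cohort.
- State that the results are descriptive, because there is no control arm and the disease itself impairs growth.

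The cost is one derived variable per measure and one extra table. No new visit, sample or test is needed. The main limitation is that Z-scores end at the upper age of the chosen reference, and some patients will reach adult age during the study.
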